## **4.2 Method of Assigning Patients to Treatment Groups**

### **4.2.1 Recruitment**

Approximately 25-30 sites will participate in this trial.

Each trial site will require potential patients to undergo a Screening Visit prior to randomisation to a treatment group. Each patient will receive a unique screening number which must be entered in a screening log that must be maintained at each trial site. The screening number will be allocated sequentially in the order in which the patients are screened. The results of each screening should be recorded in the screening log. Selected data for screened patients should also be entered in the electronic case record form (e-CRF), along with the reason for screening failure if the patient is not randomised to treatment.

Under no circumstances will patients screened in the trial be permitted to be re-screened for a second time in this trial, except who need Run-in Period to stabilize the dose of concomitant treatment per protocol.

### **4.2.2 Randomisation**

After all applicable screening assessments have been performed, patients who have met all inclusion criteria and none of the exclusion criteria will be centrally, dynamically, randomly allocated to one of the three groups and will receive a unique computer-generated randomisation number.

At the Randomisation Visit (Visit 2), patients will be centrally, dynamically randomised in a 1:1:1 fashion to each of the three arms, namely placebo, TJ301 300 mg, or TJ301 600 mg, by validated Interactive Web Response System (IWRS). Randomisation will be stratified by prior corticosteroids treatment (yes/no) and consent to participate in PK substudy (yes/no). . This information will be

collected at Visit 1 and will be used at Visit 2 for randomisation by stratification based on these factors.

In addition, only some patients in Mainland China will enter the PK subgroup. Patients in PK subgroup (N=24, 8 for each arm) will be centrally, dynamically randomised in a 1:1:1 fashion to each of the three arms, namely placebo, TJ301 300 mg, or TJ301 600 mg.

### **4.3 Restrictions**

#### **4.3.1 Prior and Concomitant Therapies**

Details of all concomitant medication will be recorded in the e-CRF, along with the main reason for prescription. In addition, prior treatment for UC within 12 months of Visit 1 (Screening) will be recorded.

#### **4.3.2 Prohibited Therapy**

Patients will be prohibited from taking any other IMP or undergo any other investigative treatment during the trial from the time the informed consent form is signed through to at least the Follow-up Visit, or any other IMP within 30 days or 5 half-lives prior to Visit 2 (whichever is longer).

The following previous or concomitant medications are disallowed during the trial:

- Immunomodulating/suppressing drugs, including JAK inhibitors (NB: AZA and 6-MP are allowed as per inclusion criteria, see Section 4.1.1).
- Antibiotics, when given as treatment for UC relapse.
- Any biologic drugs.
- Any live (attenuated) vaccines.

#### **4.3.3 Other Restrictions**

Patients on stable-dose concomitant treatment for UC at Visit 2 must remain on a stable dose throughout the trial except for patients on corticosteroids; tapering of corticosteroids is allowed at the discretion of the Investigator.

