##### 3.1.2 Overall Design

This is a multicenter, stratified randomized, double-blind, placebo-controlled phase II study.

The trial includes a Run-in Period (if stable conventional treatment needed), a 4-week Screening Period, a 12-week double-blind Treatment Period, and a Safety Follow-up Period of 3 weeks to Day 105.

90 patients will be centrally, dynamically, randomly assigned to 3 groups (1:1:1) to receive 600mg TJ301 biweekly (Q2W), 300mg TJ301 Q2W or placebo Q2W. Randomisation will be stratified by prior corticosteroids treatment (yes/no) and consent to participate in PK substudy (yes/no). TJ301 or placebo administrations will occur on Days 0, 14, 28, 42, 56, and 70.

During the double-blind period and the follow-up period, patients should be on stable conventional treatment for UC.

There will be 9 ~ 10 main visits at the investigational site during the study:

- Visit 0: Run-in Period: at an optional visit (Visit 0), decision will be made if patients need stable conventional UC treatment to meet the following criteria: with corticosteroids stable for at least 2 weeks prior to Randomization at no more than 20 mg prednisone (or equivalent), and/or with medications containing 5-aminosalicylates (5-ASA) at no less than 2 g 5-ASA per day for at least 3 months and stable for at least 4 weeks prior to Randomization, and/or with azathioprine (AZA) at no less than 1.5 mg/kg/day or mercaptopurine (6-MP) at no less than 0.75 mg/kg/day for at least 6 months and stable for at least 6 weeks prior to Randomization. If patients already met the criteria, they will directly enter the Screening Period (Visit 1). If not, they will need stable conventional UC treatment during the Run-in Period except those who cannot tolerate the medications mentioned above.
- Visit 1: Screening Visit, start of Screening Period (Days -28 to -1 prior to Visit 2)
- Visit 2: Randomisation Visit (Baseline), start of 12-week Double-blind Treatment Period
- Visits 3-7: 5 visits during 12-week Double-blind Treatment Period
- Visit 8: End of Treatment (EoT) Visit, completion of 12-week Double-blind Treatment Period
- Visit 9: Safety Follow-up Visit, scheduled at 35 days after the last dose of IMP (Day 105).

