### 3.4 Discussion of Overall Trial Design

#### 3.4.1 Trial Design

This trial is designed as a randomised, double-blind, placebo-controlled proof-of-concept trial of TJ301. Patients will be on concomitant treatment with stable doses of corticosteroids, or immunomodulators, or 5-ASA/sulfasalazine – all first- or second-line standard of care in UC – for at least the duration of the 12-week Treatment Period (i.e. up to the primary endpoint). Two dose levels of TJ301 will be investigated, and as discussed in Section 3.4.4, modelling of the effect on a PD biomarker, based on PK measurements over a wide range of serum concentrations of TJ301, suggests that the chosen dosages may show a dose-dependent clinical efficacy.

The typical duration of induction treatment in active UC, both in clinical practice and in clinical trials, is at least 8 weeks. The novel mechanism of action with TJ301, with blockade of only IL-6 *trans*-signalling, may influence the time to a clinically relevant endpoint such as clinical remission. In order to capture the full extent of the potential treatment effect, the primary endpoint will be assessed at Week 12. As shown in the recent proof-of-concept trial with etrolizumab (10) in a

similar trial population as the one proposed with TJ301, placebo response was higher earlier during the treatment course (at Week 6 as opposed to Week 10). Thus, more substantive ‘true’ response and remission rates can be expected with longer treatment duration.

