### **4.4 Withdrawal Criteria**

The patients have the right to withdraw from the trial at any time for any reason, without the need to justify their decision. However, the Investigator should record the reason for the patient's withdrawal, if possible. The Investigator also has the right to withdraw patients.

Patients will be withdrawn in the following circumstances:

- A patient's desire to withdraw for any reason.
- Loss to follow-up (every effort must be made to contact the patient; a certified letter must be sent or phone calls on three separate days must be made).

- An adverse event which, in the opinion of the Investigator and/or Sponsor, necessitates withdrawal.
- A patient's substantial non-compliance (e.g. visits non-compliance) after agreement with the Sponsor.
- The Investigator's opinion that continuing the patient in the trial is not appropriate. The Investigator may withdraw a patient at any time if it is considered to be in the patient's best interest.
- Patients suffering a worsening in disease after Visit 5 are to be withdrawn. Worsening will be defined as an increase from the last visit in Mayo rectal bleeding subscore  $\geq 1$ , over 3 consecutive days. Such worsening should be evaluated by the Investigator and confirmed by endoscopy (no improvement or worse) prior to deciding whether or not to withdraw the patient.

Patients discontinued from the trial will be invited to a Safety Follow-up Visit 35 days (5.8 - 6.6 half-lives of TJ301) after the last dose of IMP as soon as possible after a decision of discontinuation has been taken. At these visits, the Investigator will obtain all the required details and document the date of the premature termination and the main reason in the e-CRF.

In case the patient has withdrawn consent, no new data can be entered into the e-CRF and data are recorded in the medical records only. Correction of previous data entries and/or entering of data related to visits/procedures done prior to but made available after withdrawal of consent (e.g. laboratory results) will be allowed unless the patient disapproves it.

Any withdrawal must be fully documented in the e-CRF and source documents, registered in the e-CRF as discontinued, and followed by the Investigator/Investigative Staff. If the reason for discontinuation is an adverse event, the specific event will be recorded in the e-CRF. Withdrawn patients will not be replaced.

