### 9.1 Determination of Sample Size

This is a proof-of-concept trial not aimed at confirming evidence of primary efficacy but rather at exploring preliminary indications of efficacy (not *per se* restricted to primary only) and safety with the aim of informing a decision about proceeding into full development. The exploratory nature of this trial requires a minimum number of patients to be exposed, yet without losing the possibility of inferring meaningful conclusions.

A sample size of N=72 (n=24 per treatment/placebo arm) patients is expected to achieve a power of 83% of detecting a trend ( $p < 0.05$ , one-sided) if the true remission rate difference (at Week 12) between the placebo and highest dose groups (600 mg Q2W) is 30% (10% for the placebo and 40% for the highest dose) using Pearson's chi-square test without continuity correction. The trial also has 70% power to reach a statistically significant result ( $p < 0.05$ , one-sided) in case the remission rate difference between placebo and treatment (300 mg Q2W and 600 mg Q2W combined together) is 20% (10% vs 30%). Considering the dropout rate of approximately 20%, a total of 90 patients will be enrolled competitively.

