### **9.6.2 Primary Endpoint**

The primary efficacy endpoint is clinical and endoscopic remission (defined as a full Mayo score  $\leq 2$ , no individual subscore  $> 1$ , rectal bleeding subscore = 0) at Week 12 in the ITT population. This binary outcome (remission status=yes/no) variable will be analysed by a logistic regression model with treatment and the randomisation-stratification factors (prior corticosteroids treatment and consent to participate in PK substudy) as fixed effects and the baseline full Mayo score as covariate. A patient with missing data on the remission status will be assumed to be not in remission. Sensitivity analyses, using different analyses sets and missing data handling, will be detailed in the SAP.

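### Section 4.3.3 lets investigators taper corticosteroids at will before Week 12, contradicting the stable-dose design in 3.4.1 and 3.1.2, so a flare on taper can count as non-remission

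*Protocol*

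**What the plan says.** Three current parts of the protocol describe how background corticosteroids are handled after randomisation.

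- **Section 3.4.1 (Trial Design):** "Patients will be on concomitant treatment with stable doses of corticosteroids, or immunomodulators, or 5-ASA/sulfasalazine", and this "for at least the duration of the 12-week Treatment Period (i.e. up to the primary endpoint"). Corticosteroids are named, and the period is tied to the Week 12 endpoint.
- **Section 3.1.2 (Overall Design):** "During the double-blind period and the follow-up period, patients should be on stable conventional treatment for UC". No taper exception is given. The synopsis version exempts only patients who cannot tolerate the treatment.
- **Section 4.3.3 (Other Restrictions):** concomitant UC treatment must stay stable for the whole trial, but corticosteroids are exempt: "tapering of corticosteroids is allowed at the discretion of the Investigator".

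Four other provisions determine what a taper can do to the primary result.

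- **Endpoint (9.6.2):** full Mayo score of at most 2, no subscore above 1 and no rectal bleeding at Week 12, with no condition on corticosteroid dose.
- **Missing data (9.6.2):** "A patient with missing data on the remission status will be assumed to be not in remission".
- **Withdrawal (4.4):** "Patients suffering a worsening in disease after Visit 5 are to be withdrawn", after evaluation by the investigator and endoscopic confirmation.
- **Testing levels (9.6.1):** one-sided 5% and one-sided 20%.

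**The concern.** Section 4.3.3 is the rule that sites will follow, and it removes a condition that 3.4.1 presents as part of the design. Two investigators could treat the same patient differently and each cite the protocol. An analysis plan can describe or examine the resulting dose changes, but it cannot set dosing at the sites.

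A taper can reach the primary result by two routes. A patient who stays in the trial but has more symptoms on a lower dose fails the Mayo criteria directly; any return of rectal bleeding is enough. A patient whose worsening after Visit 5 is confirmed is to be withdrawn, and if Week 12 status is then missing, it is set to non-remission. The endpoint gives no credit for remission on a reduced dose, so tapering can cost remissions but not earn them.

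At stake are power and clarity in a proof-of-concept trial meant to inform whether to proceed to full development. A weak result could reflect the drug or uneven steroid withdrawal, and the design would not separate the two.

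**Working it through.** **1. The text.** Section 3.4.1 has stable corticosteroids from randomisation to Week 12 at least. Section 3.1.2 has stable conventional treatment throughout the double-blind and follow-up periods. Section 4.3.3 allows corticosteroid reduction at any time after Visit 2. All three are current text, so this is not a difference from superseded wording. The contradiction needs no calculation; what follows only bounds its possible effect.

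**2. Reference power.** Inputs from section 9.1: 24 per arm, "10% for the placebo and 40% for the highest dose", one-sided 5%, Pearson chi-square without continuity correction, stated power 83%.

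- Normal approximation with unpooled variance: SE = √(0.1×0.9/24 + 0.4×0.6/24) = 0.117; power = Φ(0.30/0.117 − 1.645) = 82.0%.
- Normal approximation with pooled variance: 79.0%.
- Exact enumeration of both binomials with the named test: 80.5%.

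The stated figure is reproduced to within about a point by the unpooled formula. The exact values (80.5% at one-sided 5%, 95.6% at one-sided 20%) are the baseline below. The gap from 83% is a separate matter.

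**3. Assumed loss from tapering.** The protocol gives no taper or flare rates, so all three inputs are assumptions:

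- share of patients on corticosteroids: 20% to 50%;
- share of would-be remitters on steroids tapered before Week 12: 25% to 75%;
- share of those losing remission: 20% to 50%.

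Proportion of remissions lost: k = product of the three. The same k is applied to both arms: p0 = 0.10(1 − k), p1 = 0.40(1 − k).

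| Case | k | Rates | Difference (points) | Power, 5% | Power, 20% |
|---|---|---|---|---|---|
| None | 0 | 10.0% vs 40.0% | 30.0 | 80.5% | 95.6% |
| Low | 0.20×0.25×0.20 = 0.010 | 9.9% vs 39.6% | 29.7 | 80.1% | 95.4% |
| Middle | 0.30×0.50×0.30 = 0.045 | 9.6% vs 38.2% | 28.7 | 78.5% | 94.8% |
| High | 0.50×0.75×0.50 = 0.1875 | 8.1% vs 32.5% | 24.4 | 71.1% | 91.7% |

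**4. If the loss fell on 600 mg only.** With p0 held at 0.10 and the same k applied to 600 mg alone, power at one-sided 5% is 79.8% (low) to 62.7% (high). This needs a further assumption, that tapering costs remissions only in the 600 mg arm.

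**5. Type I error.** With no drug effect, blinded tapering affects the arms alike, and prior corticosteroid use is both a stratification factor and a model term. No inflation follows.

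**The case against.** **The exception looks deliberate.** Section 4.3.3 exempts corticosteroids explicitly, whereas 3.4.1 is discussion text, and section 1.3 says that corticosteroids have frequent and sometimes serious side effects. Limiting exposure is a legitimate aim, and correcting 3.4.1, 3.1.2 and the synopsis would remove the contradiction. This stands as a reason to offer a second form of the fix. It does not justify a taper with no common schedule.

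**The effect may be small.** The middle case costs about 2 points of power at one-sided 5% and under 1 point at one-sided 20%, in a trial that section 9.6.1 calls exploratory. This stands and limits the severity.

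**Stronger readings that the protocol does not support:**

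- *Tapering shrinks the treatment difference because it follows improvement.* This is plausible under blinding, but nothing in the protocol establishes it. If the drug works, tapered placebo patients may flare proportionally more, which would offset some of the loss; the offset is limited because few placebo remissions are expected.
- *The primary model is deficient because it adjusts only for the "randomisation-stratification factors (prior corticosteroids treatment and consent to participate in PK substudy) as fixed effects" and baseline Mayo score, not for later dose changes.* Dose after randomisation may itself be affected by treatment and should not ordinarily be a covariate. This is no defect.
- *Patients who flare are misclassified.* A patient with active disease at Week 12 is correctly scored as not in remission. The difficulty is attributing the failure to the drug or to the taper.
- *Withdrawal is the main route.* It requires a rise in rectal bleeding of at least 1 over 3 consecutive days after Visit 5, plus investigator evaluation and endoscopic confirmation, so it is narrow.

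Concomitant medication is recorded at all site visits (7.3.4), so tapering can be described afterwards. That does not standardise it.

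**Conclusion.** The contradiction between 4.3.3 and sections 3.4.1 and 3.1.2 is real, and the operative rule leaves the trial without a property that its own design discussion claims. A flare on an unstandardised taper can count as non-remission at Week 12. The consequence is added noise and a possible loss of power and clarity, with no type I error inflation.

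The size is unknown. Under the assumed rates, power at one-sided 5% drops by between 0.4 points (negligible) and 9.4 points, and at one-sided 20% by between 0.2 and 3.9 points. These figures assume equal proportional loss in both arms. More frequent tapering in the arm that improves more would make the loss larger, but that is an assumption too. The change is worth making because it is cheap and restores the stated design; it is not a threat to the trial's validity.

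**What to change.** **Preferred:** bring 4.3.3 into line with 3.4.1. Suggested wording: *The corticosteroid dose at Visit 2 is kept unchanged until all Visit 8 (Week 12) assessments are complete. Earlier reduction is permitted only for intolerance or a corticosteroid-related adverse event, and its date, dose and reason are entered in the e-CRF. Tapering may begin after Visit 8.* State the post-Visit 8 taper in 3.1.2 and the synopsis as well, since both now ask for stable treatment through follow-up.

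**Alternative:** if the sponsor wants earlier tapering to limit steroid exposure, fix one schedule for all patients (start visit, trigger, step size, rule for returning to the previous dose) and correct 3.4.1, 3.1.2 and the synopsis to match.

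**Cost:** one protocol amendment with ethics approval. Concomitant medication is already collected, and the sample size (72, or 90 with dropout) does not change. Under the preferred form, steroid users stay on up to 20 mg prednisone for 12 weeks after randomisation, or 14 weeks counting the 2-week stable period before it, unless intolerance or an adverse event permits a reduction.

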### **4.4 Withdrawal Criteria**

The patients have the right to withdraw from the trial at any time for any reason, without the need to justify their decision. However, the Investigator should record the reason for the patient's withdrawal, if possible. The Investigator also has the right to withdraw patients.

Patients will be withdrawn in the following circumstances:

- A patient's desire to withdraw for any reason.
- Loss to follow-up (every effort must be made to contact the patient; a certified letter must be sent or phone calls on three separate days must be made).

- An adverse event which, in the opinion of the Investigator and/or Sponsor, necessitates withdrawal.
- A patient's substantial non-compliance (e.g. visits non-compliance) after agreement with the Sponsor.
- The Investigator's opinion that continuing the patient in the trial is not appropriate. The Investigator may withdraw a patient at any time if it is considered to be in the patient's best interest.
- Patients suffering a worsening in disease after Visit 5 are to be withdrawn. Worsening will be defined as an increase from the last visit in Mayo rectal bleeding subscore  $\geq 1$ , over 3 consecutive days. Such worsening should be evaluated by the Investigator and confirmed by endoscopy (no improvement or worse) prior to deciding whether or not to withdraw the patient.

Patients discontinued from the trial will be invited to a Safety Follow-up Visit 35 days (5.8 - 6.6 half-lives of TJ301) after the last dose of IMP as soon as possible after a decision of discontinuation has been taken. At these visits, the Investigator will obtain all the required details and document the date of the premature termination and the main reason in the e-CRF.

In case the patient has withdrawn consent, no new data can be entered into the e-CRF and data are recorded in the medical records only. Correction of previous data entries and/or entering of data related to visits/procedures done prior to but made available after withdrawal of consent (e.g. laboratory results) will be allowed unless the patient disapproves it.

Any withdrawal must be fully documented in the e-CRF and source documents, registered in the e-CRF as discontinued, and followed by the Investigator/Investigative Staff. If the reason for discontinuation is an adverse event, the specific event will be recorded in the e-CRF. Withdrawn patients will not be replaced.

In case the Investigator becomes aware of any serious adverse events (SAEs) or related non-serious adverse events in a withdrawn patient after trial completion these will be reported to the Sponsor (Section 8.5).

The Sponsor may temporarily or permanently discontinue the trial at an investigational site at any time for safety, ethical, compliance or other reasons. If this is necessary, the Sponsor will endeavour to provide advance notification to the site. If the site or trial is suspended or discontinued, the Investigator/Investigative Staff will be responsible for promptly informing the Independent Ethics Committee (IEC) that this has happened. If required by local regulations, the Sponsor will be responsible for informing the IEC of trial or site discontinuation. In such an event, all trial data and unused IMP must be returned to the Sponsor.

## 5 TREATMENTS

### 5.1 Treatments Administered

The IMP in this trial is TJ301 (15 mg/mL in solution for injection [25 mM histidine, 200 mM sucrose, 0.1 mg/mL polysorbate 20 in aqueous solution]).

- Active substance: TJ301
- Provide by: Leading Biopharm Limited
- Manufacturer: Octoplus Development B.V. (now as [name] &Development B.V.) , Netherlands
- Application form: intra-venous Infusion
- Formulation: 15 mg/mL, 5mL vials, Solution for injection
- Packaging /units per package: diluted in 250 mL 5% (w/v) glucose for infusion
- Storage (incl. specific storage guidance): TJ301 is stored at  $-20\pm 5^{\circ}\text{C}$
- Market authorisation: No

The placebo is the solution for injection [25 mM histidine, 200 mM sucrose, 0.1 mg/mL polysorbate 20 in aqueous solution] without TJ301.

- Active substance: No
- Provide by: Leading Biopharm Limited
- Manufacturer: Octoplus Development B.V. (now as [name] &Development B.V.), Netherlands
- Application form: intra-venous Infusion
- Formulation: 15 mg/mL, 5mL vials, Solution for injection
- Packaging /units per package: diluted in 250 mL 5% (w/v) glucose for infusion
- Storage (incl. specific storage guidance): Placebo is stored at  $-20\pm 5^{\circ}\text{C}$
- Market authorisation: No

Both placebo and TJ301 should be stored at  $-20\pm 5^{\circ}\text{C}$  and thawed at the site by site personnel (blind to study randomisation) and diluted in 250 mL 5% (w/v) glucose (1.03 mg/mL TJ301 for the 300 mg group, 2.07 mg/mL TJ301 for the 600 mg group and 0 mg/mL TJ301 for the placebo group ). The infusion time is 2 hours.

The following concentrations and infusion volumes of TJ301 and placebo will be used:

Dose group	Vials	Drug volume (mL)	5% (w/v) glucose(mL)	TJ301 (mg/mL)	Infusion volume (mL)
Placebo	8 vials Placebo	40	250	0	290
300 mg	4 vials Placebo and 4 vials TJ301	40	250	1.03	290
600 mg	8 vials TJ301	40	250	2.07	290

